### **6.1.2 Visit for Immunotherapy (Pre and Post surgery: Every 3 weeks $\pm$ 3 days)**

Subjects may receive up to 2 doses of immunotherapy prior to surgery and 1-3 doses post-surgery as previously described. All sequential doses will be administered three weeks ( $\pm$ 3 days) apart.

The following study evaluations will be performed **prior to immunotherapy**:

1. Confirmation of p16 positivity or other pathological evidence of oncogenic HPV infection.
2. Medical/Clinical assessment including concomitant medications/treatments.
3. Focused physical examination including, but not limited to vital signs, weight and oxygen saturation.
4. ECOG Performance Status.
5. Review of adverse events.
6. Clinical laboratory testing including, but not limited to: CBC with differential and platelet count, total serum bilirubin, alkaline phosphatase, AST (SGOT), ALT (SGPT), serum creatinine, serum electrolytes, serum calcium and serum albumin.

NOTE: If clinical screening labs (CBC and Chemistry) were performed within 72 hours prior to the subject's first immunotherapy, these labs are not required to be redrawn prior to the subject's first immunotherapy.

7. Urine  $\beta$ -HCG (for women of child bearing potential) up to 72 hours prior to visit.
8. Whole blood and serum for baseline immunologic assays.

The following study evaluations will be performed on the same day **post-immunotherapy**:

1. Injection site reaction assessment within 30-45 minutes after EP.
2. Review of adverse events.
3. Data should be downloaded from the EP device.
4. Distribute participant reminder card to be reviewed at the next visit.

### **6.1.3 Surgery**

At the time of definitive surgery, fresh resected tumor specimens not needed for diagnostic purposes and unstained slides will be collected and will be used for correlative studies and evaluation of immune responses. Prior to surgery whole blood and serum will also be collected for immunologic assays.

### **6.1.4 Post surgery 2 week follow up ( $\pm$ 7 days)**

1. Medical/Clinical assessment including concomitant medications/treatments.
2. Complete physical examination including, but not limited to vital signs, weight and oxygen saturation.
3. ECOG Performance Status.
4. Review of adverse events.
5. Whole blood and serum for immunologic assays.

### **6.1.5 Inspection Visit 4 Weeks Post-Surgery ( $\pm$ 7 days)**

1. Medical/Clinical assessment including concomitant medications/treatments
2. Complete physical examination including, but not limited to vital signs, weight and oxygen saturation.
3. ECOG Performance Status.
4. Review of adverse events.
5. Visual Inspection of wound healing.
6. Whole blood and serum for immunologic assays.

### **6.1.6 2 Week Follow Up Post Last Dose of Immunotherapy ( $\pm$ 3 Days)**

1. Medical/Clinical assessment including concomitant medications/treatments
2. Complete physical examination including, but not limited to vital signs, weight and oxygen saturation.
3. ECOG Performance Status
4. Review of adverse events.
5. Clinical laboratory testing including, but not limited to: CBC with differential and platelet count, total serum bilirubin, alkaline phosphatase, AST (SGOT), ALT (SGPT), serum creatinine, serum electrolytes, serum calcium, serum albumin and CPK.
6. Injection site reaction assessment.
7. Whole blood and serum for immunologic assays.

### **6.1.7 Long term follow up (every 3 months $\pm$ 7 days for 6 months)/End of study visit**

**Long term follow up for 6 months from the last dose of immunotherapy. End of study visit will be the last long term follow up visit.**

1. Medical/Clinical assessment including concomitant medications/treatments.
2. Complete physical examination including, but not limited to vital signs, weight and oxygen saturation.
3. ECOG Performance Status.
4. Review of adverse events.
5. Clinical laboratory testing including, but not limited to: CBC with differential and platelet count, total serum bilirubin, alkaline phosphatase, AST (SGOT), ALT (SGPT), serum creatinine, serum electrolytes, serum calcium and serum albumin.
6. Whole blood and serum for immunologic assays.

## **6.2 Cohort II**

Immunotherapy will start approximately 2-6 months after completion of chemoradiation therapy.

### **6.2.1 Pre-treatment evaluation (Screening; within 28 days of first dose)**

1. Signed written informed consent.
2. Complete medical history including prior and concurrent medications/treatments.
3. Complete physical examination including, but not limited to vital signs, height, weight and oxygen saturation.
4. ECOG Performance Status.
5. Tumor Evaluation: Confirmation of diagnosis by histology and confirmation of p16 and HPV -16 and/or -18 (by PCR or ISH assay) positivity.
6. 12-lead ECG (performed up to 4 weeks prior to Dose 1).
7. Clinical laboratory testing including, but not limited to: CBC with differential and platelet count, PT, INR/PTT, total serum bilirubin, alkaline phosphatase, AST (SGOT), ALT (SGPT), serum creatinine, serum electrolytes, serum calcium and serum albumin and CPK

Note: If these testing are performed within 28 days prior to study Day 0 as standard of care, the results can be used for screening and eligibility assessment.

8. Serology (HIV Ab, HCV Ab, HBsAg).
9. Serum beta HCG (for women of child bearing potential)
10. Whole blood and serum for baseline immunologic assays.
11. Paraffin-embedded tumor tissue or unstained slides for IHC.

If clinical screening labs (CBC and Chemistry) were performed within 72 hours prior to the subject's first immunotherapy, these labs are not required to be redrawn prior to the subject's first immunotherapy.

### **6.2.2 Visit for Immunotherapy (4 doses Every 3 Weeks $\pm$ 3 days)**

The following study evaluations will be performed **prior to immunotherapy:**

1. Medical/Clinical assessment including concurrent medications/treatments.
2. Focused physical examination including, but not limited to vital signs, weight and oxygen saturation.
3. ECOG Performance Status.
4. Review of adverse events.
5. Clinical laboratory testing including but not limited to: CBC with differential and platelet count, total serum bilirubin, alkaline phosphatase, AST (SGOT), ALT (SGPT), serum creatinine, serum electrolytes, serum calcium and serum albumin. Urine  $\beta$ -HCG (for women of child bearing potential).

NOTE: If clinical screening labs (CBC and Chemistry) were performed within 72 hours prior to the subject's first immunotherapy, these labs are not required to be redrawn prior to the subject's first immunotherapy.

6. Whole blood and serum for baseline immunologic assays.

The following study evaluations will be performed on the same day **post-immunotherapy:**

1. Injection site reaction assessment within 30-45 minutes after EP.
2. Review of adverse events.
3. Data should be downloaded from the EP device
4. Distribute participant reminder card to be reviewed at the next visit.

### **6.2.3 2 Week Follow Up Post Last Dose of Immunotherapy ( $\pm$ 3 days)**

1. Medical/Clinical assessment including concurrent medications/treatments.
2. Complete physical examination including, but not limited to vital signs, weight and oxygen saturation.
3. ECOG Performance Status.
4. Review of adverse events.
5. Injection site reaction assessment.
6. Clinical laboratory testing including but not limited to: CBC with differential and platelet count, total serum bilirubin, alkaline phosphatase, AST (SGOT), ALT (SGPT), serum creatinine, serum electrolytes, serum calcium, serum albumin and CPK.
7. Whole blood and serum for immunologic assays.

### **6.2.4 Long Term Follow Up (Every 3 Months $\pm$ 7 Days for 6 months)/End of study visit Long term follow up for 6 monthss post the last dose of immunotherapy. End of study visit will be the last long term follow up visit**

1. Medical/Clinical assessment including concurrent medications/treatments.

2. Complete physical examination including, but not limited to vital signs, weight and oxygen saturation.
3. ECOG Performance Status.
4. Review of adverse events.
5. Clinical laboratory testing including, but not limited to: CBC with differential and platelet count, total serum bilirubin, alkaline phosphatase, AST (SGOT), ALT (SGPT), serum creatinine, serum electrolytes, serum calcium and serum albumin.
6. Whole blood and serum for immunologic assays.

## **6.3 Timing and Evaluation**

### **6.3.1 Informed Consent**

Study personnel will meet with prospective study subjects, explain the study, and provide them with an informed consent form (ICF) that describes the screening tests, eligibility criteria for entering the study, and study treatments and follow-up procedures. The subjects must sign the ICF before the study can commence.

### **6.3.2 Assignment of Subject Numbers**

Study personnel will screen subjects and assign allocation numbers as appropriate. Each subject who consents will be assigned a patient identification number (PIN) which identifies the subject for all study-related procedures for the duration of their participation in the study. Once assigned, PINs cannot be reused for any reason.

### **6.3.3 Medical History/Existing Events/Illnesses**

Investigators should document all relevant and clinically significant non-cancer related illnesses that the subject has experienced within 5 years prior to screening and all prior cancer related illnesses as Medical History. The determination of the relevance includes, but not limited to, the history related to HNSCCa and treatment for HNSCCa, major surgery and procedures, on-going medical conditions that require continuous treatment or close follow up/monitoring, history of hypersensitivity and allergic events.

Illnesses' first occurring or detected after the ICF is signed or during the study and/or worsening of an existing illness during the study are to be documented as AEs on the CRF.

Prior treatments, defined as administered prior to first immunotherapy treatment, should be recorded in the CRF as prior medications. Concomitant treatments, defined as treatments continued by the subject upon entry into the study and new treatments taken after the first immunotherapy treatment, should be recorded in the CRF as concomitant medications.

The subject's previous anti-cancer treatments, including detailed information about their therapy directed against HNSCCa (e.g. past surgical and/or radiation regimens) should be documented. Additionally, information about any non-cancer treatments should also be noted.

### **6.3.4 Safety Assessments**

The following subject evaluations for safety will be performed.

#### **6.3.4.1 Participant Reminder Card**

Subjects record any post treatment reactions and enter this information on the participant reminder card. The study staff will review the reminder card and assess the reported events for clinical significance.

Study staff should evaluate each unique reminder card entry according to CTCAE guidelines (Version 4.03) and Table 6.1 of the protocol, “Grading Scale for Injection Site Reactions.” Any reminder card entry determined to meet the criteria for a Grade 1 or higher adverse event should be documented as an adverse event unless deemed part of the subject’s ongoing medical history. If the reminder card entry does not meet the criteria of a Grade 1 or higher AE as per the CTCAE guidelines, clinical judgment can be used to determine whether the entry should be recorded as an AE and documented accordingly in the site’s source. For cases where the reminder card entry and final AE reporting (i.e. grading) do not agree, the reasoning should be recorded in the source documents.

#### **6.3.4.2 Medical/Clinical Assessments and concomitant medications**

New onset disease and concomitant medications will be queried from the first time reported through to the end of study visit/discharge.

Assessment of adverse events will be collected from the time of informed consent through End of Study visit and will be assessed using the “Common Terminology Criteria for Adverse Events (CTCAE)”, version 4.03 issued by the US Department of Health and Human Services on June 14, 2010.

#### **6.3.4.3 Physical Assessments**

A complete physical examination will be conducted at specified visits. A targeted physical assessment will be performed at other visit as determined by the Investigator or directed per subject complaints. The injection site is to be assessed by the study personnel within 30 – 45 minutes after EP, and during subsequent clinic visits as specified in the schedule of events (Tables S1 and S2).

#### **6.3.4.4 Vital Signs**

Vital signs may include but are not limited to, body temperature, oxygen saturation, blood pressure and heart rate will be measured at specified visits.

#### **6.3.4.5 Weight and Height**

Weight (kg) and height (cm) will be collected at specified visits. The information can be used for body mass index (BMI) calculations.

#### **6.3.4.6 12-Lead ECGs**

An ECG will be performed within 28 days of the first dose of immunotherapy for eligibility.

#### **6.3.4.7 Pregnancy Test**

Women of reproductive potential must have a negative serum  $\beta$ -HCG test at screening and a negative serum or urine (with sensitivity of at least 25 mIU/mL)  $\beta$ -HCG within 72 hours prior to administration of immunotherapy. If at any point the  $\beta$ -HCG test is positive, indicating that the subject is pregnant, no additional immunotherapy will be administered, but the subject will be followed for the duration of the study and beyond to determine the outcome of the pregnancy (with the subject’s consent).

#### **6.3.4.8 Eastern Cooperative Oncology Group (ECOG)**

ECOG performance status will be measured at specified visits.

#### **6.3.4.9 Laboratory Evaluations**

Blood samples will be taken to be tested for serum chemistry and complete blood count as specified in the Schedule of Events (Tables S1 and S2).

##### Complete Blood Count

White blood cell (WBC) count with differential, Red blood cell (RBC) count, Hemoglobin, Hematocrit, Platelet count and PT, INR/PTT (screening only).

##### Serum Chemistry

Bilirubin, alkaline phosphatase, SGPT (serum glutamic-pyruvic transaminase)/ALT, SGOT (serum glutamic-oxaloacetic transaminase)/AST, creatinine, electrolytes, calcium, albumin and CPK (at screening and at 2 weeks after the last dose of immunotherapy only).

##### Serology (screening only):

Antibody to human immunodeficiency virus (HIV-Ab), hepatitis B surface antigen (HBsAg), antibody to hepatitis C virus (HCV)

### **6.4 Optional collection of Leftover Tumor Tissue Sample**

Leftover tumor tissue samples may be collected through subject's standard of care during the course of the study. The tumor tissue samples will be used for immunological and correlative assessments.

### **6.5 HLA Testing**

HLA testing will be performed on PBMC from any single blood sample collected for immunogenicity analysis after screening visit. If the subject has a record of previous high resolution HLA testing and access to results, this HLA testing is not required.

The DNA extracted from the blood sample will be used to determine if alleles at the MHC locus affect the immune response to study treatment. Data arising from this study will be subject to same confidentiality as the rest of the study. This specimen will be destroyed immediately after the analysis and the results checked.

### **6.6 Injection of INO-3112 Followed by Electroporation**

INO-3112 will be administered, mixed in a volume of 1.1 mL by IM injection in the deltoid followed immediately by EP. If the deltoid is not a suitable location, the IM injection should be in the lateral quadriceps followed immediately by EP. Vaccination/EP must not be given within 2 cm of a tattoo, scar, or active lesion/rash or on the same side of the body where an implanted device is located. The timing of the initial dose will be as outlined above.

The vaccination/electroporation procedure will be performed by qualified personnel. An individual designated to perform the procedure should be permitted by the relevant local authorities to administer parenteral injections to subjects (licensed health care professionals who have appropriate credentials, e.g. MD, DO, RN, NP, PA) in addition to satisfactorily completing device training from device company personnel. Individuals whose credentials do not meet the relevant local requirements may perform the /electroporation procedure under one or both of the conditions below:

1. The procedure must be performed under the direct supervision of the Principal Investigator or an approved Sub-Investigator who has already been trained by device company personnel.
2. The CV and any relevant qualifications of the individual have been reviewed and approved by the device company or its designee to perform the procedure.

Any deviation from the above procedures must be approved by the Inovio Pharmaceuticals, Inc. or its designee.

### 6.6.1 Management of anxiety and pain due to EP procedure

Subjects will be offered topical anesthetic (e.g. EMLA), to limit significant discomfort from the vaccination/EP procedure. If EMLA (lidocaine 2.5% and prilocaine 2.5%) is used, an approximately 1.5 cm diameter amount will be applied with occlusion to the site of injection ~30 minutes prior to vaccination/EP. Subjects will be offered an analgesic (e.g. ibuprofen, ketorolac) after vaccination/EP. In case subjects are anxious for the procedure, they will be offered a mild sedative (e.g. 0.5-1.0 mg lorazepam), or equivalent, as a mild sedative for anxiety related to the vaccination/EP procedure. Mild sedatives may be administered approximately 1 hour prior to EP. Subjects who receive a mild sedative should not operate a motor vehicle for 3-4 hours after receiving medication and should have arranged transportation to depart the study site. Subjects who are allergic to or have contraindications to EMLA, ibuprofen, ketorolac or a mild sedative will be offered a suitable alternative.

### 6.6.2 Assessment of Injection Site Reactions

When evaluating injection site reactions throughout the study, the investigator or designee will be instructed to use the following grading scale (Table 6.1):

**Table 6.1: Grading Scale for Injection Site Reactions**

| Local Reaction to Injectable Product (Grade) | Mild(1)                                | Moderate(2)   | Severe(3)   | Potentially Life Threatening(4)       |
|---|---|--|--|--|
| Pain  | Does not interfere with activity              | Repeated use of non-narcotic pain reliever >24 hours or interferes with activity | Any use of narcotic pain reliever or prevents daily activity | Emergency room (ER) visit or hospitalization |
| Tenderness  | Mild discomfort to touch                      | Discomfort with movement   | Significant discomfort at rest                               | ER visit or hospitalization                  |
| Erythema/Redness*                                   | 2.5-5 cm                                      | 5.1-10 cm  | >10 cm   | Necrosis or exfoliative dermatitis           |
| Induration/Swelling*                                | 2.5-5 cm and does not interfere with activity | 5.1-10 cm or interferes with activity  | >10 cm or prevents daily activity                            | Necrosis                                     |

\* September 2007 “FDA Guidance for Industry—Toxicity Grading Scale for Healthy Adult and Adolescent Volunteers Enrolled in Preventive Vaccine Clinical Trials”

\*in addition to grading the measured local reaction at the greatest single diameter, the measurement should be recorded as a continuous variable

\*\*Induration/Swelling should be evaluated and graded using the functional scale as well as the actual measurement

## 7 Statistical Plan

### 7.1 Sample Size Determination

A minimal of 20 but no more than 25 eligible subjects will be enrolled, as described above. This study is an estimation study, and as such, a power calculation is not applicable. Regarding the primary analysis, 20 subjects will provide 95% confidence that the true incidence of SAEs is <17% if 0 SAEs are observed. If more than one subject in a cohort discontinues early for reasons other than toxicity from the immunotherapy, consideration will be given for replacement.

### 7.2 Statistical Methods

The primary analysis will estimate safety parameters. The incidence of SAEs and the incidence of injection site reactions will be estimated along with exact Clopper Pearson 95% confidence intervals. Toxicity experience will also be recorded and summarized.

In secondary analyses, immune response parameters will be estimated. For continuous outcomes, the mean and 95% confidence interval will be calculated using a t-distribution approach, and for binary outcomes, the proportion and exact Clopper Pearson 95% confidence interval will be calculated.

In exploratory analyses, we will also estimate the distributions of progression-free survival (PFS) and overall survival (OS) will be estimated, and any observed anti-tumor responses will be summarized. PFS and OS will be measured from the time of instillation of the initial dose of immunotherapy. Both The variables will be potentially censored by the end of the subject's observation. These distributions will be summarized using Kaplan-Meier survival curves and estimated median time to event of each type. Anti-tumor response category frequencies will be calculated.

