## SUMMARY OF CHANGES

The following is a list of significant protocol changes from v2.0 dated June 25, 2015 to v2.1 dated April 8, 2016. All other changes are administrative and do not significantly affect the safety of subjects, study scope, or scientific quality of the protocol.

1. The long term follow up period post last dose is changed from "2 years from screening" to "6 months post the last dose of immunotherapy". It is mainly because to date, safety profile from 19 subjects who have been followed for more than 6 months does not show any study treatment related adverse safety events, therefore it is considered an undue burden on subjects to continue the follow up for an extended time period.  
Following sections of the protocol are affected:

- Protocol Synopsis
- Tables S1 and S2 Schedule of Events
- Section 3, Study Design
- Section 6.1.7 Cohort I Long Term Follow Up
- Section 6.2.4 Cohort II, Long Term Follow Up

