Despite the availability of highly curative treatments, at least 10-30% of patients with HPV related HNSCCa (depending on smoking status and other unknown variables) will eventually develop locally recurrent and/or metastatic disease. The prognosis of patients with locally recurrent or metastatic HNSCCa is dismal, and palliative treatment options remain extremely limited. A few patients with recurrent disease are candidates for salvage therapies, including potentially curative surgery [7]. Highly selected patients in this setting may benefit from re-irradiation although the morbidity of this approach is substantial [8]. Palliative systemic therapy remains the mainstay for most patients. Despite the availability of cytotoxic chemotherapy and targeted agents like cetuximab, median survival for patients with incurable HNSCCa is around 10.5 months [9].

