## 2.3 Exploratory Objectives

1. Explore anti-tumor response
2. Explore progression free survival

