## 3 Study Design

This will be a prospective, open-label, Phase I/IIa study of immunotherapy with INO-3112 in subjects with HPV-positive HNSCCa. Subjects will receive a course of treatment as described below and will be followed for safety as well as immune and clinical responses for 6 months from the last dose of immunotherapy.

The safety and effects of immunotherapy will be studied in two populations:

1. In chemo- and radiation-naïve subjects who undergo definitive surgery and
2. In subjects after chemoradiation therapy.

Doses of INO-3112 are based on safety experience in prior and on-going clinical trials. Based on the prior experience with these agents, dose escalation will not be conducted in this trial.

The study is divided into the following treatment cohorts:

- I. INO-3112 (6 mg VGX-3100 + 1 mg INO-9012) will be given to subjects before and after definitive surgery.
- II. INO-3112 (6mg VGX-3100 + 1 mg INO-9012) will be given to subjects after chemoradiation therapy.

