## **4.4 Early Withdrawal of Subjects**

### **4.4.1 When and How to Withdraw Subjects**

Subjects who do not complete the study protocol will be considered to have prematurely discontinued the study. The reasons for premature discontinuation (for example, voluntary withdrawal, toxicity, death) must be recorded on the case report form (CRF). Final study evaluations will be completed at the time of discontinuation if it is possible. Reasons for withdrawal include, but are not limited to the following:

1. Inter-current illness that would, in the judgment of the investigator, affect assessments of clinical status to a significant degree or require discontinuation of study;
2. Unacceptable toxicity: Subjects will be followed until resolution or stabilization;
3. Disease progression;
4. Subject withdraws consent;
5. Treatment delay greater than four weeks for any toxicity;
6. Subjects who do not have satisfactory compliance with study procedures;
7. Major protocol violations, including, but not limited to:
  - a. failure to meet major inclusion/exclusion criteria;
  - b. failure to complete full evaluations as required by protocol;
  - c. use of concomitant therapies.

If any subject in a cohort discontinues early for reasons other than toxicity from immunotherapy, consideration will be given for replacement.

If a subject discontinues Study Treatments before completion of long term follow up for 6 months post the last dose of immunotherapy, all assessments for the end of Study Treatment visit and/or end of study visit should be performed.

Subjects who have disease progression confirmed and/or start new anti-cancer therapy will be discontinued from the study. In both Cohorts, subjects who progress in their disease, once confirmed, will be required to come for the end of the study visit. All subjects will be followed for survival status regardless of the cause of death.

In the case of a fatal outcome, all relevant information (including cause of death, autopsy report, ER/hospital record, concomitant medication, and relationship to Study Treatment or underlying disease) will be collected.

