### 7.3 Subject Population(s) for Analysis

Any subject who receives at least one dose of treatment will be included in the safety analyses. For immunogenicity and survival/anti-tumor analyses, the main analyses will utilize subjects who received their assigned number of doses.

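### Limiting the main PFS and OS analyses to subjects who received all assigned doses, while timing from dose 1, biases these exploratory curves modestly upward; section 7.2 also gives them no interval

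*Combined protocol and SAP*

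**What the plan says.** PFS is an exploratory objective (section 2.3: "Explore progression free survival"). OS is not among the endpoints in section 3.2 and enters only in section 7.2. There, both are timed from the first dose and censored at the end of the subject's observation, and the output is described in one sentence: "These distributions will be summarized using Kaplan-Meier survival curves and estimated median time to event of each type". The same section names 95% intervals for the safety and immune estimates, but none for PFS or OS.

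Section 7.3 puts anyone with at least one dose into the safety analyses. For the rest it says: "For immunogenicity and survival/anti-tumor analyses, the main analyses will utilize subjects who received their assigned number of doses".

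Section 4.4.1 says: "Subjects who have disease progression confirmed and/or start new anti-cancer therapy will be discontinued from the study". Under section 3, subjects are "followed for safety as well as immune and clinical responses for 6 months from the last dose of immunotherapy". The Summary of Changes shows that this replaced a rule of "2 years from screening" and cites the "safety profile from 19 subjects who have been followed for more than 6 months". The only recurrence figure is background in section 1.1.1: "at least 10-30% of patients with HPV related HNSCCa" eventually relapse, with no time horizon.

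**The concern.** Membership of the main survival set is decided by something that happens after the clock starts. Receiving every dose requires staying alive and, in effect, without confirmed progression until the last dose. The early events are removed, while the event-free time of everyone else before the last dose is kept. This is immortal-time selection. Its direction follows from sections 4.4.1, 7.2 and 7.3 together and needs no model; only its size does.

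At stake is how an uncontrolled curve from 20 to 25 subjects is read. Without a stated interval, a reader has no prompt to see how imprecise the curve is, and the main set makes it look better than the experience of all dosed subjects. No primary or secondary conclusion depends on it.

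**Working it through.** **The plan's own figure.** Section 7.1 gives none for PFS or OS. Its one figure, an SAE rate below 17% if 0 of 20 subjects have one, reproduces as the Clopper-Pearson upper limit: 1 - 0.025^(1/20) = 16.8%.

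**Timing.** The assigned number of doses is taken as 4 in both cohorts.
- Cohort II: 4 doses 3 weeks apart put dose 4 at day 3 × 21 = 63. The last visit falls near day 63 + 183 = 246.
- Cohort I, latest case: one dose before surgery, surgery at day 28 (the end of the usual 2-4 weeks in section 3.1), dosing resumed 28 days later (assumed, at the inspection visit), then two more 21-day intervals. Dose 4 is at day 28 + 28 + 42 = 98.

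**Size of the bias at 6 months (day 183).** Assume a constant event rate with a proportion p having an event by day h, so S(t) = (1 - p)^(t/h). All dosed subjects give S(183). If every event before dose 4 (day d) removes the subject at once, completers give S(183)/S(d). If confirmation lags by L days, only events before day d - L are removed, and completers give S(183)/S(d - L).

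| Scenario | All dosed | Cohort II, d = 63, no lag | Cohort I, d = 98, no lag |
|---|---|---|---|
| p = 30% by day 246 | 76.7% | 76.7/0.913 = 84.0% (+7.3) | 76.7/0.868 = 88.4% (+11.7) |
| p = 10% by day 246 | 92.5% | 92.5/0.973 = 95.0% (+2.5) | 92.5/0.959 = 96.4% (+4.0) |
| p = 30% by day 730 | 91.5% | 91.5/0.970 = 94.3% (+2.9) | 91.5/0.953 = 95.9% (+4.5) |

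With a lag of 3 or 6 weeks (assumed) in Cohort II:
- p = 30% by day 246: 76.7/0.941 = 81.5% (+4.8), or 76.7/0.970 = 79.1% (+2.4).
- p = 30% by day 730: 93.3% (+1.9), or 92.4% (+0.9).

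**Would a PFS median be reached?** Put the whole background risk inside current follow-up, which favours reaching it. With equal follow-up, the chance that at least half have an event is:
- n = 20: P(Bin(20, p) ≥ 10) = 4.8% at p = 30% and 0.26% at 20%.
- n = 25: P(Bin(25, 0.3) ≥ 13) = 1.7%.
- n = 20 at an assumed 40%: 24%.

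Simulating staggered last visits (day 260-281 in Cohort I, day 230-262 in Cohort II) with n = 20 and 30% by day 246 gives about 10% in all dosed subjects and about 4% in completers.

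The actual follow-up of the 19 earlier subjects is not given. If it is assumed to run up to day 700 for 19 of 20:
- 30% recurring by day 700 gives 5-9%.
- The rate of 30% by day 246 continuing to day 700 means 1 - 0.7^(700/246) = 64% recurring, above the background range, and gives 73-92%.

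**Precision at a fixed time (Clopper-Pearson, nobody censored).** 17/20 = 85% (62-97%); 9/10 = 90% (56-99.7%); 5/5 = 100% (48-100%).

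**The case against.** The case against has real force.

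A Kaplan-Meier curve already shows the event-free proportion at every time, and a median that is not reached is a valid result. For an exploratory endpoint, a missing landmark and interval are reporting detail. That stands, so they are only a small addition here.

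A reader might take 77% against 84-88% as the expected distortion. The documents do not support that. It puts the top of an eventual rate into about 8 months and removes every early progressor at once. Table S1 lists tumor evaluation only at screening, Table S2 lists none, section 3.1 leaves tumor status to standard of care, and section 4.4.1 requires progression to be confirmed. A progressor could receive dose 4 before confirmation and stay in the set with the event counted. The 88% also needs day 98, which only Cohort I reaches. Beside an interval 35 points wide for 17/20, a shift of 1-3 points is small.

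A reader might also infer that the median will not be reached. That depends on a background rate worded as a minimum with no horizon, and on unknown follow-up of 19 earlier subjects. Nor does it carry over to OS: sections 4.4.1 and 4.4.2 follow survival status in all subjects with no stated end.

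Finally, section 7.3 speaks of main analyses, so an analysis of all dosed subjects is not ruled out. None is specified, however. The direction of the bias in the main set survives all of this.

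**Conclusion.** The analysis-set point holds: as written, the main PFS curve is biased upward, and OS in the same direction because deaths before the last dose also leave the set. For PFS at 6 months the size is about 1-3 points on Cohort II timing if 30% recur over 24 months. The upper end is about 7 points in Cohort II and 12 in Cohort I, if 30% recur within about 8 months and removal is immediate. A 3- to 6-week confirmation lag brings the Cohort II upper figure down to about 2-5 points. All sizes rest on a constant event rate and the timings above.

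The absence of an interval and a fixed-time estimate is a lesser gap. If the 10-30% rate applies within current follow-up, a PFS median would probably not be reached (about a 5-10% chance or less at n = 20); longer follow-up of earlier subjects could change that. Severity is minor: exploratory endpoints only.

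**What to change.** **Section 7.3.** Make all subjects with at least one dose, the set already used for safety, the main set for PFS and OS. At the least, report it beside the completer set, with each labelled.

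**Section 7.2.** Add the Kaplan-Meier PFS estimate at one pre-stated time within planned follow-up, with a 95% CI and number at risk, by one standard method (for example log-log, with an exact interval when there are no events). Report the median if reached.

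**Reconcile.** Section 3.1 provides for adjuvant chemotherapy or radiation after immunotherapy in Cohort I, while section 4.4.1 discontinues subjects who start new anti-cancer therapy. The text should say whether adjuvant therapy counts as such, because Cohort I censoring depends on it.

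**Cost.** A few sentences and no added visits. The PFS curve will look slightly less favourable and the intervals will be wide. If 6 months from dose 1 is chosen, it falls between the Cohort II visits near day 63 + 91 = 154 and day 246. Progression between days 154 and 183 but first found at day 246 would count as event-free at 6 months: S(154) - S(183) = 1.2 to 3.3 points for 10-30% by day 246, if no standard-of-care assessment falls between. With 19 subjects already followed in an open-label study, the gain from pre-specifying the time is limited; the gain from the all-dosed set is not affected.
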